6.3 Participant Identification Procedures and Eligibility Criteria

6.3.1 Historical Control Group:

Reintubation rates are tracked at the institutional level as part of quality assessments; a delegated member of the study team will utilize this patient list to generate a study-specific subset of high-risk patients who were mechanically ventilated between February and October 2019. This list will be screened for the inclusion/exclusion criteria below by a delegated member of the study team. The study statistician or designee will then use a random number generator to generate a final group of 80 patients that meet inclusion criteria.

Inclusion Criteria

1. Age ≥ 18 years
2. Chronic cardiac or pulmonary condition
 - o COPD, history of based on any documentation notes
 - o CHF, history of based on any documentation notes
 - o Positive fluid balance, defined as a positive number when calculating fluid input minus fluid output over the approximate 24-hour-period prior to extubation
3. Documented modified RSBI between 58-105 on the day of extubation

Exclusion Criteria

1. Patients receiving comfort care or terminal extubation
2. Home ventilator, based on any documentation notes
3. Only primary extubations will be included (i.e., if the patient list query identifies multiple mechanical ventilations, only the primary encounter/event will be included)

6.3.2 Prospective Group:

An EMR-based report of all patients that have been on mechanical ventilation (MV) at Grant Medical Center for at least 24 hours will be generated daily (Monday through Friday), per standard procedure. Eligibility determination for this cohort will be conducted by a delegated member of the study team across two time points: pre-screening to determine eligibility to approach for consent, and eligibility on the day of extubation to determine enrollment eligibility (Appendix A). Only patients meeting all required eligibility criteria above will be enrolled to the study; any PHI collected for patients that are not subsequently enrolled will be destroyed after non-eligibility determination.

Pre-Screening Criteria:

1. No home ventilator, based on any documentation notes
2. Not scheduled for terminal extubation/comfort care
3. Has not had a failed extubation during the current hospital stay
4. Has not previously participated in the current trial
5. Any other reason, at the discretion of the study team/clinical care staff, that should preclude the LARs being approached. These include, but are not limited to, facial trauma or other severe injuries that make extubation unlikely or that would make BiPAP contraindicated. Because patients will be screened daily, it is possible that a patient that fails pre-screening earlier in the stay may be eligible for enrollment later in their stay. This is okay.

Day of Extubation Criteria

1. Patient/LAR provided informed consent
2. Documented high-risk factors of interest (CHF, COPD, and/or positive fluid balance) as defined for the historical control cohort
3. The modified RSBI must be between 58-105
4. Patient must successfully complete spontaneous breathing trial and be determined eligible for extubation
5. Patient must not have extubated themselves
6. The patient must have no other contraindication that would preclude the postextubation protocol (e.g., facial trauma, tracheotomy, or any other reason that would preclude use of BiPAP or HFNC)
7. The patient must not be undergoing terminal extubation or placed on comfort care

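### Controls come from the reintubation-tracking list and are screened with no masking or record cut-off, so the screener can know the primary outcome while judging note-based eligibility

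*Combined protocol and SAP*

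**What the plan says.** Section 6.3.1 (Historical Control Group) sets out three steps.

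1. Source: "Reintubation rates are tracked at the institutional level as part of quality assessments; a delegated member of the study team will utilize this patient list". From it comes a high-risk subset ventilated between February and October 2019.
2. Screening: "This list will be screened for the inclusion/exclusion criteria below by a delegated member of the study team".
3. Selection: the statistician or a designee then draws 80 at random from those who meet the criteria.

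Several criteria depend on reading the chart: "COPD, history of based on any documentation notes", "CHF, history of based on any documentation notes" and, as an exclusion, "Home ventilator, based on any documentation notes". Comfort care is also an exclusion, with no time point attached for controls. Other criteria are recorded values: age, "Documented modified RSBI between 58-105 on the day of extubation", and "Positive fluid balance, defined as a positive number when calculating fluid input minus fluid output over the approximate 24-hour-period prior to extubation". The third exclusion shows that repeat episodes can appear on the list: "if the patient list query identifies multiple mechanical ventilations, only the primary encounter/event will be included".

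For the prospective group, Section 6.3.2 starts from a daily report of ventilated patients and settles eligibility, including comfort care, on the day of extubation. The primary analysis in Section 7.1.1 compares reintubation within 72 hours between the two groups.

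**The concern.** In the prospective group, eligibility is judged before reintubation can have happened. In the control group it is judged months later, from a list kept because of reintubation, with the whole chart open. No section masks the screener, limits the records by date, asks for a second screener, or requires a log of excluded controls. The one restriction on data access, in Section 8.1, is that statisticians receive de-identified data, and this does not reach the screener.

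The screener need not act in bad faith for this to matter. A reintubated patient plausibly has a longer stay and more notes, and so more chances for COPD or CHF to be mentioned. That would raise the control rate and flatter the protocol. In the other direction, a comfort-care decision made after reintubation could remove a reintubated control, although the same event could not make an enrolled patient ineligible. That would lower the control rate.

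The control rate matters beyond the test. Section 4 treats it as the institution's baseline in this population, and Section 3.1 says the data will be used to plan a larger randomised trial.

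**Working it through.** **Order of steps.** The list is built, then screened, then sampled. A simple random sample represents the pool it is drawn from. If the pool has been shaped by the outcome, the sample of 80 inherits that.

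**Where judgement enters.**
- Little or none: age, modified RSBI on the day of extubation, and fluid balance (a calculated sign, loose only in its approximate 24-hour window).
- Some: COPD, CHF and home ventilator (any note, no date limit), and comfort care (no time point).
- A patient with a positive fluid balance meets inclusion criterion 2 whatever the notes say about COPD or CHF.

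**Illustration.** The plan gives no assumed control rate, effect size or power, so there is no figure of its own to reproduce.

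Inputs from the plan: 40 intervention patients and up to 80 controls (Section 5); significance at p ≤ 0.05 (Section 7.1, taken as two-sided).

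Assumed: a true rate of p = 0.20 in both groups. Section 3.2 cites 12-14% for planned extubations generally, 19% and 23% in the arms of a high-risk trial, and 35-67% in older patients with severe chronic disease. Let r be the probability that a non-reintubated patient is found eligible, relative to an otherwise equivalent reintubated one.

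Control rate = p / (p + (1 − p) r).

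The mechanism acts only on patients whose eligibility turns on a judged item. If that is 30% of the non-reintubated (an assumption), and r = 0.8 among them, the overall value is 0.70 × 1 + 0.30 × 0.8 = 0.94. The upper case applies r = 0.8 to everyone.

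- r = 1: control rate 20.0%.
- r = 0.94: 0.20 / (0.20 + 0.752) = 21.0%.
- r = 0.8: 0.20 / (0.20 + 0.64) = 23.8%.

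The chance of a significant result falsely favouring the intervention was found by enumerating all outcomes of 40 v 80. The test was an unadjusted chi-square, or Fisher's exact test where an expected count was below 5.

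| Overall r | Control rate | False-benefit chance |
|---|---|---|
| 1 | 20.0% | 2.2% |
| 0.94 | 21.0% | 2.9% |
| 0.8 | 23.8% | 6.1% |

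At r = 0.8 with other true rates (13%, 19%, 23%, 35%, 67%), the control rate rises by 2.7, 3.7, 4.2, 5.2 and 4.7 percentage points, and the false-benefit chance is 4.4%, 5.9%, 6.6%, 7.8% and 8.1%.

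**Opposite direction.** If reintubated patients are the ones lost, with relative eligibility s, the control rate is ps / (ps + 1 − p). For s = 0.94 it is 0.188 / 0.988 = 19.0%; for s = 0.8 it is 0.16 / 0.96 = 16.7%. The protocol would then look worse than it is.

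**The case against.** **The list's fields are not described.** A reader might infer that the screener sees a reintubation flag beside each name. The documents do not say so. They give the list's purpose and show that repeat ventilations may appear on it. Appendix F, the control data tool, is visible only by title and could contain safeguards. This stands: visibility is inferred. The claim is that the screener can know the outcome, not that the list displays it; unrestricted chart review would reveal it in any case.

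**Most of eligibility is recorded.** RSBI and age bind every control, and positive fluid balance alone satisfies criterion 2. A single mention in any note is also a low threshold, and Section 6.3.2 uses the same risk-factor definitions for the prospective group. This stands and narrows the exposure. It does not remove it, because a low threshold with no date limit still rewards a longer search or a thicker chart.

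**The size is hypothetical.** A relative eligibility of 0.7 across the whole cohort would give a control rate of 26.3% and a false-benefit chance of 10.7%, but nothing in the documents supports so large a loss. The planned primary analysis is also a covariate-adjusted logistic regression, not the unadjusted test used here. Both points stand, although covariate adjustment cannot be relied on to correct selection on the outcome.

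**This is an exploratory pilot, and open chart review is usual for historical controls.** That is true and limits the weight of the point. The affected comparison is nonetheless the primary one, and the protection is cheap.

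A smaller qualification: under Section 6.6, analysis of prospective patients also depends on the protocol having been ordered and initiated, which is settled after extubation. Their eligibility is still fixed on the day of extubation.

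**Conclusion.** The concern holds in limited form. Section 6.3.1 leaves the primary outcome open to the person judging control eligibility, the prospective group has no such exposure, and the random draw comes too late to help. The risk is confined to patients whose eligibility turns on COPD, CHF, home ventilator or comfort care.

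A reader might go further and conclude that the control rate will be inflated, or that the comparison is invalid. The documents support neither: they do not show that selection will occur, and its direction is unknown.

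If selection favours the intervention, the illustrated range is a control rate of 21.0% to 23.8% instead of 20%, and a false-benefit chance of about 3% to 6% instead of 2.2%. This rests on an assumed true rate of 20%, an assumed relative eligibility of 0.94 to 0.8, no true effect, and an unadjusted test. The procedure should be changed, because the weakness is avoidable and bears on the primary comparison.

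**What to change.** Amend Section 6.3.1 to fix the order of work:

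1. The person who builds the list identifies each patient's first planned extubation and passes on the list without reintubation status or later ventilation episodes.
2. A different delegated team member judges every criterion, including comfort care, only from records dated up to that extubation, and locks eligibility.
3. The statistician draws the sample from the locked list.
4. Only then is the outcome abstracted.

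The cost is modest. Section 6.3.1 already provides for a list-builder, a screener and a statistician, but the first two must now be different people. The screener must also keep to a cut-off in a chart that continues past it, so masking may be imperfect.

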4 SPECIFIC AIMS

The purpose of this study is to establish baseline data regarding the institutional reintubation rate in a specific, high-risk patient population of interest and to determine the preliminary effectiveness of a standardized intermittent NIV/HFNC protocol in patients considered high risk for reintubation. This is a prospective, non-randomized exploratory trial with the following specific aim(s):

Aim 1. Compare reintubation rates (within 72 hours) between patients that undergo a standardized, intermittent NIV/HFNC protocol and a historical control cohort.

Aim 2. Determine whether reintubation rates differ as a function of age, gender, co-morbidity, reason for intubation, service line/operative status, or modified RSBI.

Secondary aims include calculating length of stay (ICU and total hospital), total ventilator time, in-hospital mortality rate, adverse event rates, and 30-day readmission rate. The overall demographics of the interventional group will also be compared to the historical control cohort.

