5 STUDY POPULATION AND SAMPLE SIZE

There are approximately 3-4 patients per business day (Monday through Friday) that require mechanical ventilation at OhioHealth Grant Medical Center, resulting in approximately 80 patients per month. An estimated 30% of these patients are high risk, resulting in an estimated 24 high-risk patients per month.

A historical control cohort will consist of up to 80 randomly selected high-risk patients that underwent planned extubation in an OhioHealth Grant Medical Center Intensive Care Unit prior to initiation of the prospective cohort.

For the prospective, interventional cohort we plan to consent all adult mechanically ventilated patients that meet pre-screening criteria in order to obtain a final sample size of 40 enrolled patients who meet all criteria on the day of extubation. We anticipate this will result in up to 240 patients consented and 40 patients enrolled over approximately 12 weeks; however, this time period can be extended if needed to obtain 40 patients in the final data set.

See [Section 6.3](#) for detailed inclusion/exclusion criteria.

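### Section 6.3.1 screens the whole 2019 control list, then keeps only 80 eligible patients at random without saying why; if more than 80 qualify, the baseline reintubation rate is less precise than it need be.

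*Combined protocol and SAP*

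**What the plan says.** Section 6.3.1 sets out three steps for the historical controls. A list is built of "high-risk patients who were mechanically ventilated between February and October 2019". Then: "This list will be screened for the inclusion/exclusion criteria below by a delegated member of the study team". Only after that does the statistician act, who "will then use a random number generator to generate a final group of 80 patients that meet inclusion criteria". The same section notes: "Reintubation rates are tracked at the institutional level as part of quality assessments".

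Section 5 words the number as a ceiling: "A historical control cohort will consist of up to 80 randomly selected high-risk patients that underwent planned extubation". Section 6.2 also gives 80 as a maximum. Neither section gives a reason for 80.

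Section 5 supplies the volumes: 3 to 4 ventilated patients per business day, "resulting in approximately 80 patients per month", with 30% at high risk, "resulting in an estimated 24 high-risk patients per month". It expects up to 240 patients consented to yield 40 enrolled over about 12 weeks.

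Section 4 opens the study's purpose with the aim to "establish baseline data regarding the institutional reintubation rate in a specific, high-risk patient population of interest". Aim 1, the comparison of 72-hour reintubation with the historical cohort, follows.

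**The concern.** The draw comes after eligibility screening, so it saves none of the screening work. If more than 80 patients pass, the surplus is set aside although the site has already identified them as eligible. What is lost is precision, first in the control group's reintubation rate, which Section 4 names as a purpose in its own right and which would feed the planning of the larger randomized trial described in Section 3.1. The comparison with the 40 treated patients is affected too, but less. Because the number eligible is not to be reported, a reader of the results could not tell whether anything had been dropped.

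**Working it through.** **The plan's own figures.** The 80 cannot be reproduced, because the documents give no planning rate, effect size, power or precision target for it. The accrual figures do reproduce: 0.30 × 80 = 24 high-risk patients per month, and 80 × 3 months = 240.

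**How many controls might qualify.** No count is given, so this is an inference with a range.
- Monthly volume: 80 (Section 5), or about 65 if the lower daily figure applies (3 × 21.7 business days, the 21.7 being an assumption).
- Window: 9 months if February and October both count, 7 if only the months between them do.
- Yield: 40/240 = 1/6 (Section 5), assumed to carry over to 2019.

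Eligible = volume × months × 1/6:
- 80 × 9 / 6 = 120
- 65 × 9 / 6 = 97.5, about 98
- 80 × 7 / 6 = 93
- 65 × 7 / 6 = 76, where the cap does not bind

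An upper bound is 24 × 9 = 216. It counts high-risk ventilated patients before the RSBI, planned-extubation and exclusion criteria are applied.

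The draw would set aside 0 of 76, 18 of 98 (18%) or 40 of 120 (33%).

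**Precision of the baseline rate.** The 95% half-width is 1.96 × √(p(1 − p)/n), in percentage points. The rates are illustrative: Section 3.2 cites 12 to 14% for planned extubations in general, 19% and 23% on NIV and HFNC in high-risk patients, and 35 to 67% in older patients with severe chronic disease.

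| Assumed rate | n = 80 | n = 98 | n = 120 | n = 216 (bound) |
|---|---|---|---|---|
| 13% | 7.4 | 6.7 | 6.0 | 4.5 |
| 20% | 8.8 | 7.9 | 7.2 | 5.3 |
| 35% | 10.5 | 9.4 | 8.5 | 6.4 |
| 50% | 11.0 | 9.9 | 8.9 | 6.7 |

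Relative to 80 controls, the standard error is multiplied by √(80/98) = 0.90 or √(80/120) = 0.82.

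**Precision of the comparison.** With 40 treated patients and equal rates, the ratio of standard errors against 80 controls is √[(1/40 + 1/n)/(1/40 + 1/80)]:
- n = 98: 0.969, about 3% lower
- n = 120: 0.943, about 6% lower
- n = 216: 0.889, about 11% lower
- unlimited controls: √[(1/40)/(1/40 + 1/80)] = 0.816, so never more than 18% lower

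For illustration, with 35% against 19% and a two-sided 5% test (sidedness assumed), power is 43.5% with 80 controls and 47.1% with 120.

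**The case against.** The best defence is that the cap may cost little or nothing. Sections 5 and 6.2 give 80 as a maximum, the low end of the inferred pool is below it, and missing RSBI documentation in 2019 could reduce the pool further. The 1/6 yield describes prospective patients who had already passed pre-screening and faced somewhat different criteria, so it may not transfer in either direction. Each further control also needs chart abstraction, and workload is a plausible unstated reason for the cap. In an exploratory study there is no precision target to miss. All of this stands. It limits the size of the point, but it does not explain why 80 was chosen or why the eligible count should go unreported.

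Four stronger readings are tempting, and the documents do not support them.
- A reader might take 216 as the eligible pool and conclude that nearly two thirds (136 of 216) are discarded. That figure precedes several eligibility criteria and is only a bound.
- A reader might infer that each listed record already holds the 72-hour outcome. Section 6.3.1 says only that rates are tracked at institutional level, and Section 7 has study data taken from the medical record.
- A reader might suspect bias. A simple random draw from the eligible patients introduces none.
- A reader might fault the draw for not balancing the groups. Using every eligible control would not balance them either. Section 7.1.1 deals with imbalance by covariate adjustment.

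**Conclusion.** The point holds as one of efficiency and reporting. Screening everyone and then keeping 80 has no stated justification and, if more than 80 qualify, gives away precision on a stated purpose. On the inferred pool of about 76 to 120, the baseline half-width could shrink by anything from nothing to 1.6 points at a 20% rate (8.8 to 7.2) or 2.0 points at 35% (10.5 to 8.5).

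For Aim 1 the gain is about 0 to 6% in standard error, because the 40 treated patients dominate. It would not change what the comparison can show.

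These sizes rest on three assumptions: 2019 volumes like those in Section 5, a yield of one in six, and the illustrative rates. The recommendation does not depend on them, since it costs nothing extra when 80 or fewer qualify. This is an inexpensive improvement and does not call the study's validity into question.

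**What to change.** In Section 6.3.1, and in the matching ceiling in Sections 5 and 6.2:
1. State that the number of screened patients found eligible will be reported.
2. Estimate the 72-hour reintubation rate on all eligible screened controls.
3. Use that same full set in the adjusted primary comparison of Section 7.1.1, so that there is one control set.
4. If covariate abstraction has to be capped at 80, keep the random draw for the adjusted model, give the reason, and present the all-eligible rate as the baseline figure.

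Cost: no additional patient is enrolled. The 72-hour outcome must be abstracted for perhaps 0 to 40 more charts (136 at the upper bound: 216 − 80). The covariates are needed for the same charts if the full set enters the adjusted model. If institutional tracking proves to hold reintubation times by patient, the outcome part becomes lighter, but the documents do not establish that.

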6.2 Study Groups

Historical Control Group (Group 1): The historical control group will consist of up to 80 mechanically ventilated patients with documented presence of one or more chronic cardiac or pulmonary conditions that underwent planned extubation during the study period and meet all inclusion criteria outlined below.

Interventional Group (Group 2): The interventional group will consist of up to 40 patients for whom the LAR provides informed consent and who meet all study eligibility criteria.

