9.4 Clinical Trial of an FDA-Regulated Device

This study meets the FDAAA 801 definition of an "Applicable Clinical Trial" of devices regulated by the United States Food and Drug Administration (FDA) and must therefore be registered on ClinicalTrials.gov. The Principal Investigator or designee will register and activate the study account prior to enrollment, the informed consent form will be posted within 60 days of the last patient enrollment, and all results will be entered within 12 months of the Primary Completion Date (PCD), which is the date of final data collection for the primary outcome measure (e.g., after the last enrolled patient is first extubated, regardless of whether or not they need to be reintubated).

The medical devices used in this study are lawfully marketed in the United States and are being used in accordance with current, FDA-approved labeling for the population of interest (Appendix E). The designed trial is not intended to support a new indication of the devices or to support a change in the labeling. The investigators will obtain IRB approval as well as informed consent before enrolling each prospective patient in the trial.

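### The index extubation that starts the 72-hour clock is chosen by different rules in the two groups, which can bias the Aim 1 comparison; the likely size is modest and the direction unknown

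*Combined protocol and SAP*

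**What the plan says.** Aim 1 (Section 4) is to "Compare reintubation rates (within 72 hours) between patients that undergo a standardized, intermittent NIV/HFNC protocol and a historical control cohort".

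**Controls.** Section 6.3.1, third exclusion criterion, limits the cohort to primary extubations and adds that "if the patient list query identifies multiple mechanical ventilations, only the primary encounter/event will be included". *Primary* is not defined. Section 6.2 describes controls as patients who "underwent planned extubation during the study period".

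**Prospective group.** Two of the pre-screening criteria in Section 6.3.2 bear on earlier events: "Has not had a failed extubation during the current hospital stay" and "Has not previously participated in the current trial". *Failed extubation* is not defined. The day-of-extubation list rules out self-extubation ("Patient must not have extubated themselves") but does not require a first extubation and does not repeat the bar on a failed one. Screening is daily, and the section notes that "it is possible that a patient that fails pre-screening earlier in the stay may be eligible for enrollment later in their stay".

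**Elsewhere.** Section 9.4, explaining the registry's Primary Completion Date, gives as an example the time "after the last enrolled patient is first extubated, regardless of whether or not they need to be reintubated". Section 7.1.1 analyses reintubation within 72 hours and in separate windows, the last running from beyond 72 hours to 7 days.

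**The concern.** Every reintubation window is counted from the index extubation, so the two groups should reach that time point by the same rule. Here one group is limited to the primary event and the other is limited only by the absence of an earlier failure. Patients on a later ventilation episode can thus be present in one group and absent from the other. If they are reintubated more often than first-episode patients, the intervention rate is raised and a real benefit is understated. If less often, the benefit is overstated.

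Section 7.1.1 relies on logistic regression with statistically significant baseline characteristics as covariates. Episode number is not among the characteristics named in Aim 2. Even if it were recorded, no control would have a later-episode index, so for these patients the effect of the episode cannot be separated from the effect of treatment. An episode indicator could only remove them from the treatment contrast, which amounts to restricting the analysis to first episodes.

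**Working it through.** **Step 1. Apply each rule to the same patient histories** (reading *primary* as first).

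| History within one stay | Control, 6.3.1 | Prospective, 6.3.2 |
|---|---|---|
| One episode, planned extubation | That extubation | That extubation |
| First extubation failed, ventilated again | First extubation only | Later entry barred by pre-screening criterion 3 |
| First extubation did not fail, ventilated again, not enrolled the first time | First extubation if it meets the other criteria; on this reading, otherwise not included | Later extubation can be the index |
| Reintubated more than 72 hours after the first extubation | As above | Depends on whether this counts as failed, which is not stated |

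The rules agree in the first row, and in the second neither group can be indexed on the later episode. They part in the third and possibly the fourth. A prospective patient could miss enrolment at the first extubation for ordinary reasons in the plan: under 24 hours of ventilation, no consent yet, or a modified RSBI outside 58-105.

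**Step 2. Inputs for size.** The plan states no power or effect size, so there is no design figure to reproduce.
- Group sizes: 40 and up to 80 (Section 5).
- Reintubation rate p: 21%, the middle of the 19% and 23% in Section 3.2. As a higher case, 35%, the lower end of the range given there for older patients with severe chronic disease.
- Share f of the 40 indexed on a later episode: 2-15%, assumed.
- Risk ratio RR, later against first episode: 1.25-2.5, assumed.

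**Step 3. Shift in the intervention rate** = f × p × (RR − 1).
- p = 21%, low: 0.02 × 0.21 × 0.25 = 0.00105, or 0.1 points. High: 0.15 × 0.21 × 1.5 = 0.04725, or 4.7 points (1.9 of 40 patients).
- p halved to 10.5%: 0.02 × 0.105 × 0.25 = 0.0005, or 0.05 points; 0.15 × 0.105 × 1.5 = 0.0236, or 2.4 points (0.9 of 40 patients).
- p = 35%: 0.02 × 0.35 × 0.25 = 0.00175, or 0.2 points; 0.15 × 0.35 × 1.5 = 0.0788, or 7.9 points.

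The 21% line describes an intervention with no effect on a 21% rate. The halved line is the relevant one for the worry that a real benefit is understated.

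**Step 4. Compare with sampling error.**
- Both rates 21%: √(0.21 × 0.79 × (1/40 + 1/80)) = 0.079, or 7.9 points. The largest shift is 4.7/7.9 = 0.60 of this.
- 21% against 10.5%: √(0.21 × 0.79/80 + 0.105 × 0.895/40) = 0.067, or 6.7 points. The largest shift is 2.4/6.7 = 0.36 of this.
- Both rates 35%: √(0.35 × 0.65 × (1/40 + 1/80)) = 0.092, or 9.2 points. The largest shift is 0.85 of this.

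**Step 5. Effect on power, for scale only.** With a true halving of 21%, two-sided 0.05 and a normal approximation, power is 35% with no shift, 28% at f = 10% and RR = 2, and 21% at f = 15% and RR = 2.5.

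**The case against.** The strongest reply is that the main route to bias is already closed. Criterion 3 keeps out anyone whose extubation failed earlier in the stay, criterion 4 prevents repeat entry, and both groups need a planned extubation. What remains is a patient who came through one extubation, was ventilated again for at least 24 hours, and then met consent, risk-factor and RSBI requirements. That may be very few people, and their risk need not be higher. This stands, and it limits the size of the problem.

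It can also be said that the gap depends on undefined terms. Staff might treat reintubation after 72 hours as a failure, since Section 7.1.1 tracks it to 7 days, and *primary* might not mean first. The data collection tools in Appendices A and F, whose contents are not in the text reviewed, might settle this. These are fair cautions, but they are reasons to write the definition down. They do not remove the difference between the two stated rules.

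The Section 9.4 wording suggests a common intent, but it is an example for a registry date, not an eligibility criterion, and may mean first extubated on study.

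Three stronger inferences are not supported. A reader might conclude that the comparison is biased against the intervention; the documents give no share, risk or direction. A reader might take the sentence on later eligibility as permission to enrol on second episodes; it concerns only patients who fail pre-screening and later pass, and a failed extubation keeps failing criterion 3 for that stay. A reader might extend the point to length of stay and ventilator time; a control ventilated again after the index can also carry both episodes into hospital and ICU stay, so no clear asymmetry is shown.

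**Conclusion.** The concern holds as a conflict between two stated rules that can bias Aim 1. It is not demonstrated bias. It rests on reading *primary* as first and on some prospective patients having an earlier extubation that did not count as failed.

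Under the assumed shares and risk ratios the shift is about 0.1 to 4.7 points at a 21% intervention rate and 0.05 to 2.4 points at half that rate. It is below one standard error throughout, including the 35% case, and well below it over most of the range. The direction follows the unknown later-episode risk. Power is low before any shift, and the plan is exploratory with no power claim, so the power figures do not make this a major defect. The correction is still worth making: the error would be systematic, the results are meant to inform a randomized trial, and the remedy is cheap.

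**What to change.** 1. Use one index-extubation rule in Sections 6.3.1 and 6.3.2: the first planned extubation in the stay that meets all criteria and was not preceded by a failed extubation in that stay, one per patient, chosen without reference to what happened afterwards. State that the 72-hour clock starts there in both groups.
2. Define *primary* (if the word is kept) and *failed extubation* identically for both groups, and say whether reintubation after 72 hours counts as failure. Without this, the common rule keeps the present ambiguity.
3. Repeat the failed-extubation check among the day-of-extubation criteria.
4. If enrolment is complete, apply the same rule to the 2019 control list, or add a 72-hour analysis restricted to first-episode patients in both groups. Report how many prospective patients were indexed on a later episode.

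Cost: a few sentences of protocol text, and review of each ventilation episode on the control list instead of only the first. The restricted analysis would lose a few of the 40 prospective patients (up to 6 at the assumed 15%). No new procedures or visits are needed.
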